#### **C.4. Research Design and Methods**

**C.4.a: Project Overview:** The Wills Eye Glaucoma Research Center will conduct a 5-year prospective, randomized controlled trial to evaluate an innovative, community intervention using posterior fundus photographs of the optic nerve and macula to improve access and utilization of eye care to detect, treat, and manage high-risk patients with previously undiagnosed glaucoma, glaucoma suspect, and other eye diseases. L. [name]; [name]; and [name], RD, will lead the research study.

Our diverse targeted, at-risk population includes African Americans, Hispanics, and Asians over age 40; other older adults (aged 65+); individuals over age 40 with a family history of glaucoma and/or with diabetes. Approximately 1250 patients will be recruited from geographically diverse locations across Philadelphia and Chester counties, with the help of our community partners. **Phase 1** will consist of detecting eye disease in 7

primary care offices and 10 FQHC using telemedicine (Visit 1), followed by a comprehensive eye exam by a Wills glaucoma specialist in the same setting to confirm the diagnosis (Visit 2). Based on preliminary data, 30% of patients (approximately 750) will have abnormal optic nerve and/or macula images. The predictive accuracy of the optic nerve images to detect glaucoma and glaucoma suspect as confirmed by the comprehensive eye exam will be evaluated.

**Phase 2** will involve consenting, enrolling, and randomizing 374 patients to either the usual care group (n=187) or the enhanced intervention group (n=187). The enhanced intervention will consist of using patient navigators and a social worker to reduce barriers to follow-up eye care. **Phase 3** will consist of following patients proximally (6 months) and distally (3 years) while they attend appointments with a local, eye care provider (Visits 3-7). Adherence to follow-up recommendations for eye care will be the primary outcome measure. A comprehensive cost study to estimate the intervention costs and cost-effectiveness of detecting eye diseases and vision impairment in a high-risk population will also be conducted. Protocols, materials, outcomes, and results will be disseminated to other communities in order to expand detection of glaucoma, other eye diseases, and visual impairment, and to further refine these approaches to successfully scale the program up to a national level.

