**C.7. Enhanced Intervention Versus Usual Care Group:**

*Group 1: Enhanced Intervention Group with Patient Navigation and Social Worker:* Patients randomized to Group 1 will be provided a list of eye care providers to choose from for follow-up. Patients can also choose to follow-up with an eye care provider not on our list. In that instance we would require a record release to be signed by the patient for the purpose of having access to their follow-up records throughout the study. Prior to all follow-up visits, patients in the enhanced group who have scheduled an appointment will receive a personal phone call reminding them to attend. These patients will receive any necessary interpretation services and educational materials.

*Group 2: Usual Care:* Patients randomized to Group 2 will be recommended to follow-up for eye care with a local eye care provider. These patients will be provided a list of eye care providers to choose from for follow-up. Patients can also choose to follow-up with an eye care provider not on our list. In that instance we would require a record release to be signed by the patient for the purpose of having access to their follow-up records throughout the study. Group 2 represents a realistic choice currently available for patients. Practice patterns will vary depending on the resources, staff time, and services available within each local eye care providers practice.

**C.7.a. Sample Size Determination:** As shown in Figure 1, we have based our sample-size calculations on the current preliminary CDC-project results as well as telemedicine statistics. We project that 30% of those fundus photographs will be abnormal and that, of those, 40% of patients will likely agree to consent and enroll in the study. These patients will be randomized to either the Enhanced Intervention Group 1 or Usual Care Group 2.

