## D. EVALUATION/PERFORMANCE MEASUREMENTS

We have created distal and proximal follow-up protocols to measure public health outcomes during Phases 1, 2, and 3, with the capacity to improve quality of vision and eye health and quality-of-life in real-life settings. Outcomes may vary among our study populations depending on the diagnosis and follow-up recommendations. We have developed the research project within the *RE-AIM Framework*, as described below and focus on integrating into the vision and eye care systems of each of our partners. Westat will assist with to the evaluation process.

D.1.a. Reach: The number of patients from our partners’ primary care offices and health centers who have not seen an ophthalmologist in the past year is estimated to be more than 10,000. We conservatively estimate that 2,500 of these patients will schedule, attend, and participate in Visit 1 in the primary care setting, where we will detect glaucoma and other eye diseases using telemedicine. Based on previous demonstration projects, 2,500 patients is a reasonable and realistic number to recruit. The proportion of patients who are African American,

Caucasian, Hispanic, and Asian at each partner organization is described in the Facilities section. We will report on the demographics of the study sample, defined as the similarity to or differences between participants and eligible people who do not enroll. If differences exist in the demographic variables between our intervention and control group, our intervention may be less generalizable in other patient populations. If differences do not exist, then a stronger case can be made for generalizing the intervention into additional settings.

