**Table 9: Assessment of Adherence to Follow-Up Recommendations**

Recommended Follow-up	Number of visits per year considered adherent to recommendations
1-2 months	At least 6 visits per year with an eye care provider
3-6 months	At least 3 visits per year with an eye care provider
6 months	At least 2 visits per year with an eye care provider
12 months	At least 1 visit per year with an eye care provider

E.2.c. Primary Analysis for Aim 2: The primary outcome of the study is adherence to recommended follow-up in each year as described in section E.1.c. For each of the 3 years of follow-up, we have a dichotomous measure of adherence. We will model this longitudinal dichotomous outcome using Poisson regression within a generalized estimating equation (GEE) framework. Our model will include time (Year 1, 2, and 3), randomization assignment, randomization by treatment interaction, and baseline individual characteristics believed to be associated with adherence to follow-up, including age, diagnosis, vision impairment, and overall vision-related quality-of-life. Within this model, we will test 2 hypotheses.

First, we will compare randomization groups at Year 1 to test whether there are differences in early adherence. Second, we will calculate the average effect of randomization across Years 2 and 3 and test the long-term efficacy of the intervention. In both cases, we will estimate the overall relative risk of adherence along with its associated confidence interval. Each test will be performed with alpha=0.025. The primary analysis will include all patients who were randomized and have some adherence data (see section on missing data below).

E.2.d. Power for the Primary Analysis for Aim 2: Our estimated available sample size is given in Figure 2. We will randomize 300 patients (150 per group). Assuming up to 10% dropout where adherence cannot be calculated due to death or study withdrawal (i.e., final analysis dataset of n=135 per group), we calculate power to detect a 20% improvement in adherence under various assumptions of adherence under Usual Care. We have greater than 80% power to detect these differences using a two-sided chi-square test with alpha=0.025 (Table 10).

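### The plan states two screening numbers (1,250 and 2,500) and two randomisation targets (374 and 300), and the 750 that C.4.a calls 30% of patients is not 30% of 1,250

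*Combined protocol and SAP*

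**What the plan says.** C.4.a (Project Overview) gives three figures:

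- Recruitment: "Approximately 1250 patients will be recruited from geographically diverse locations across Philadelphia and Chester counties".
- Abnormal images: "30% of patients (approximately 750) will have abnormal optic nerve and/or macula images".
- Phase 2: "consenting, enrolling, and randomizing 374 patients to either the usual care group (n=187) or the enhanced intervention group (n=187").

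D.1.a (Reach) gives a different number for the same Visit 1 detection step in primary care: "We conservatively estimate that 2,500 of these patients will schedule, attend, and participate in Visit 1". It adds that "2,500 patients is a reasonable and realistic number to recruit".

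C.7.a (Sample Size Determination) supplies the yields: "We project that 30% of those fundus photographs will be abnormal" and, "of those, 40% of patients will likely agree to consent and enroll in the study".

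E.2.d (Power for the Primary Analysis for Aim 2) says "We will randomize 300 patients (150 per group"). It then allows for up to 10% dropout, leaving 135 per group, and reports power in Table 10 for a two-sided chi-square test at alpha 0.025.

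C.7.c names two sites whose patients are not randomised: all go to usual care at one and all to the intervention at the other. E.2.a expects 250 patients for Aim 1, about half of those with eye pathology who return for Visit 2.

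**The concern.** The size of the primary randomised comparison is stated as two numbers, and so is the screening number that feeds it. All of these statements are current text, and nothing in the text reconciles them. C.4.a is also inconsistent within itself, because its 750 does not follow from its own 1,250 and 30%.

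E.2.d is clear that Table 10 describes 300 randomised. What is unclear is which enrolment target is current. If recruitment stops at 300, a reader of E.2.d sees a completed trial and a reader of C.4.a sees a shortfall of 74. The DSMB, which is to review recruitment and enrolment reports, has no single number to compare them with. The screening number also bears on feasibility, because halving it at fixed yields halves the number randomised.

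**Working it through.** **Inputs.** Screened: 1,250 (C.4.a) or 2,500 (D.1.a). Abnormal images: 30% (C.4.a, C.7.a). Consent among those: 40% (C.7.a). Randomised: 374 (C.4.a) or 300 (E.2.d). Dropout: 10%. Alpha: 0.025, two-sided. Difference: 20 percentage points, with usual-care adherence from 35% to 60% (E.2.d, Table 10).

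**Recruitment chain** (screened × 30% × 40%, then × 0.90 / 2 per group)

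- From 2,500: 2,500 × 0.30 = 750; 750 × 0.40 = 300; 300 × 0.90 / 2 = 135 per group. This matches the 750 in C.4.a and both figures in E.2.d.
- From 1,250: 1,250 × 0.30 = 375; 375 × 0.40 = 150; 150 × 0.90 / 2 = 67.5 per group. This matches neither target. The stated 750 is 750 / 1,250 = 60% of 1,250.
- Back from 374: 374 / 0.40 / 0.30 ≈ 3,117 screened, which appears nowhere.
- Gap between targets: 374 − 300 = 74, and 74 / 300 = 25%.

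**Could 374 be 300 inflated for dropout?** No. E.2.d takes the 10% off the 300. Going from 374 to 300 would need a loss of 1 − 300/374 = 19.8%, which is not stated.

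**Where 374 may come from (inference only).** 1,250 × 0.30 = 375 and 750 × 0.50 = 375, each about 187 per group. Neither origin is stated, and neither uses the 40% in C.7.a.

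**Power.** Pooled-variance chi-square without continuity correction, with n per group and p̄ the mean of the two proportions:

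power = Φ{ [Δ − z·√(2p̄(1−p̄)/n)] / √[(p₁(1−p₁) + p₂(1−p₂))/n] }, with z = 2.241.

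Worked row, 40% against 60% at n = 135: (0.20 − 2.241 × 0.0609) / 0.0596 ≈ 1.07, so power is 85.7%. Table 10 gives 86%.

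| Usual care / enhanced | Table 10 | n = 135 (300 randomised) | n = 168 (374 randomised) | n = 67 (150 randomised) |
|---|---|---|---|---|
| 35% / 55% | 86% | 86.1% | 93.0% | 53.5% |
| 40% / 60% | 86% | 85.7% | 92.7% | 53.0% |
| 45% / 65% | 86% | 86.1% | 93.0% | 53.5% |
| 50% / 70% | 87% | 87.2% | 93.7% | 54.9% |
| 55% / 75% | 89% | 89.1% | 94.9% | 57.5% |
| 60% / 80% | 92% | 91.6% | 96.4% | 61.5% |

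The 168 is 374 × 0.90 / 2 = 168.3. Table 10 reproduces in every row at 135 per group, so it rests on 300 and not 374. Power of at least 80% in every row needs about 262 randomised (262 × 0.90 / 2 = 117.9 per group), and both targets exceed that.

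**Aim 1.** 250 / 0.50 = 500 patients with pathology returning for Visit 2. That is 20% of 2,500 or 40% of 1,250.

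**The case against.** The arithmetic is not in dispute. The fair objections concern how much follows from it.

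- *E.2.d is sound on its own terms.* This stands. The figures that do not fit are in C.4.a. E.2.d is involved only because it gives the other value of the target.
- *The 150-patient case is not a figure in the plan.* This also stands. It combines the 1,250 in C.4.a with the 40% in C.7.a and sets aside the 374. It also counts only the abnormal-image route. Patients with unreadable photographs, vision impairment or high IOP can enter too (C.5.c, C.6), in numbers the documents do not give. The 53–62% power is therefore conditional and does not carry the conclusion.
- *Aim 1 is not shown to fail.* Agreed. Eye pathology is broader than abnormal images, so 500 returning from 1,250 is not shown to be impossible. E.2.a needs only to be checked against the chosen chain.
- *The two C.7.c sites are already excluded, because both targets are worded as numbers randomised.* On a literal reading, yes, and these sites do not explain the gap. But the text never says how their enrolled patients are counted, and one sentence would settle it.
- *Figures 1 and 2 may show the intended chain.* They may; they were not available for this review. They could show which figures are current, but they cannot make C.4.a agree with D.1.a and E.2.d.

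**Conclusion.** The inconsistency is real and should be fixed. The screening number differs twofold, the randomisation target differs by 74 patients (25% of 300), and the 750 in C.4.a belongs to 2,500 and not to 1,250. The 2,500 / 750 / 300 / 135 chain is the only one in the text that closes. That does not prove it is current: the 374 could be a later change carried through only in part.

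Both stated targets support the claim of more than 80% power, under the plan's assumptions of a 20-point difference, 10% dropout and a chi-square test at alpha 0.025. If 374 is current, Table 10 is conservative.

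**What to change.** State one current screening number and one randomisation target, and use them in C.4.a, D.1.a and E.2.d. Make the abnormal-image count equal 30% of the chosen screening number. Check the consent yield in C.7.a, the Aim 1 number in E.2.a, and Figures 1 and 2 against the same chain. Report separately the patients at the two C.7.c sites, who are enrolled but not randomised, so that the target means patients actually randomised.

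If 2,500 and 300 are current, the figures to correct are the 1,250 and the 374 in C.4.a, and Table 10 stays as it is. If 374 is current, E.2.d changes, Table 10 is recomputed once at about 168 per group, and the screening number or the yields must be restated so that they lead to 374. If 1,250 is the current screening number, D.1.a and the 750 change, and the yields in C.7.a must be revised or the other entry routes quantified, because 30% and 40% alone give 150.

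The cost is wording in at most five sections (C.4.a, C.7.a, D.1.a, E.2.a, E.2.d) and at most one recomputed table. Restating the figures changes neither the design nor the analysis and calls for no extra enrolment.

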**Table 10: Determination of Power Calculation**

Percent Adherence Under Usual Care	Percent Adherent Under Enhanced Intervention	Relative Risk	Power
35%	55%	1.57	86%
40%	60%	1.5	86%
45%	65%	1.44	86%
50%	70%	1.4	87%
55%	75%	1.36	89%
60%	80%	1.33	92%

E.2.e. Secondary Analyses for Aim 2: We will perform a secondary analysis to test for differences in the average number of appointments kept per person-year of follow-up. We will use Poisson regression to model

the total number of appointments after Visit 3 by randomization assignment. The offset term will be time under observation measured from Visit 3 to end of follow-up. We will adjust baseline for age, diagnosis, vision impairment, and vision-related quality-of-life. Change in continuous clinical and quality-of-life measures (IOP, visual acuity, NEI-VFQ, etc) will be modeled using mixed effects linear regression. Fixed effects will be time (treated continuously), randomization assignment, treatment by time interaction, age, and diagnosis. A first-order autoregressive correlation structure will be assumed to model correlation among repeated measurements. When possible, random slope and intercept terms may also be included. Effects of intervention on these measures will be tested by the significance of the interaction term.

E.2.f. Exploratory Analyses for Aim 2: We will consider whether the effect of the intervention differs by baseline patient characteristics of glaucoma severity (using VF mean deviation), and vision-related quality-of-life (NEI VFQ score). The primary model will be extended to include the interaction between these variables and randomization assignment to allow for estimation of intervention effects by baseline categories.

E.2.g. Missing Data/Lost to Follow-up: Since primary outcome data will be obtained from EMRs, we do not anticipate much missing outcome data unless patients formally withdraw from the study or die during the follow-up period. For these patients, data will be missing for a year (and all years following) if they withdraw during that year of follow-up. We will fit our longitudinal models with all available data from all randomized patients. Patients who are simply lost to follow-up due to lack of contact will be considered non-adherent. Our approach to analysis provides valid estimates under the assumption that data are missing completely at random (MCAR). We will compare those who withdraw to those who do not withdraw, with respect to baseline characteristics. We will consider imputing outcomes using multiple imputations as a sensitivity analysis if it appears that the MCAR assumption is not valid. Analysis for continuous outcomes yields unbiased estimates under the missing at random assumption, and we will not impute data for these analyses.

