For each year under observation, an expected number of visits will be determined based on the recommended follow-up at the first visit for that year (Table 9). For purposes of this calculation, attendance at appointments within 13 months of the first visit will be assessed. We recognized that follow-up recommendations will vary for each patient depending on eye pressure control, medication adherence, disease severity, and surgery/laser appointments. Therefore, the research team, in conjunction with [name] and the CDC, will plan and develop definitions of adherence for patients during Visits 3-8.

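### The appointment-count model in E.2.e states no robust or over-dispersed variance, so its standard errors are likely too small if patients differ persistently in recall or in reliability of attendance

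*Combined protocol and SAP*

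**What the plan says.** Section E.2.e (Secondary Analyses for Aim 2) sets out to "test for differences in the average number of appointments kept per person-year of follow-up". The method is given as "We will use Poisson regression to model" "the total number of appointments after Visit 3 by randomization assignment", so each patient contributes one count. On exposure it says "The offset term will be time under observation measured from Visit 3 to end of follow-up". On covariates it says "We will adjust baseline for age, diagnosis, vision impairment, and vision-related quality-of-life". It names no robust variance, dispersion scale, negative binomial alternative or dispersion check, and it gives no alpha for this test.

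Table 9 sets the yearly visit thresholds. The 1-2 month recall class needs "At least 6 visits per year with an eye care provider" and the 12-month class "At least 1 visit per year with an eye care provider". Section E.2.b adds that "follow-up recommendations will vary for each patient depending on eye pressure control, medication adherence, disease severity, and surgery/laser appointments".

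GEE is specified only in E.2.c, for the yearly yes/no adherence outcome.

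**The concern.** Model-based Poisson standard errors assume that, given the covariates, the variance of a patient's count equals its mean. Two features of the plan work against that.

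- **Recall frequency.** The offset is time, not expected visits, so a patient recalled six times a year and one recalled once a year have the same expected count unless the covariates separate them. Diagnosis can do this only in part. Table 6 (section C.9) concerns a single diagnosis, POAG, yet its intervals run from 1-2 months to 12 months according to pressure control, progression and duration of control. Medication adherence and surgery or laser, which E.2.b also lists, are not covariates.
- **Reliability of attendance.** In the sponsor's chart review of patients with diabetes (section C.3.a), follow-up adherence varied with smoking (OR 0.55), insulin use (1.33), a reported A1C (1.58) and a reported glucose level (1.78). None of these is in the count model.

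What is at stake is the confidence interval for the visit-rate ratio. If it is too narrow, a chance difference in visits kept could be read as support for the navigation effect.

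**Working it through.** **The plan's own figures.** There is none for this analysis. Table 10 concerns the primary outcome; with 135 per group and two-sided alpha 0.025 it reproduces (86.1, 85.7, 86.1, 87.2, 89.1, 91.6%). It carries no information on the variance of the counts. The checks below take 135 per group and 3 years from E.2.c and E.2.d. Everything else is assumed and labelled so, including a 5% two-sided level.

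**Step 1: from dispersion to type I error.** If the variance of the counts is φ times the mean and Poisson standard errors are used, type I error = 2[1 − Φ(1.96/√φ)]. For φ = 1.25, 1.5, 2 and 3 this is 8.0, 11.0, 16.6 and 25.8%. For φ below 1 it is under 5%.

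**Step 2: what φ could be.** Let N be visits recommended over 3 years (3, 6, 9 or 18 for the four Table 9 classes), with mean m and variance v. Let p be the attendance probability, ρ the within-patient correlation of attendance, and R the share of v that the covariates explain. If kept visits cannot exceed recommended visits and recall is fixed,

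φ = (1−p) + p(1−R)·v/m + (1−p)ρ·E[N(N−1)]/m.

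Assume a 60/25/10/5% mix over 1/2/3/6 visits per year and p = 0.4:

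- m = 0.6×3 + 0.25×6 + 0.1×9 + 0.05×18 = 5.1
- E[N²] = 5.4 + 9 + 8.1 + 16.2 = 38.7, so v = 38.7 − 26.01 = 12.69 and v/m = 2.49
- E[N(N−1)]/m = (38.7 − 5.1)/5.1 = 6.59

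| R | φ (type I error), ρ = 0 | φ (type I error), ρ = 0.2 |
|---|---|---|
| 0 | 0.6 + 0.4×2.49 = 1.60 (12.1%) | 1.60 + 0.6×0.2×6.59 = 2.39 (20.4%) |
| 0.5 | 1.10 (6.1%) | 1.89 (15.4%) |
| 0.8 | 0.80 (2.8%) | 1.59 (12.0%) |

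If everyone is on 12-month recall, N = 3 and v = 0. Then φ = 0.6 at ρ = 0 (1.1%) and 0.84 at ρ = 0.2 (3.2%).

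**Step 3: simulation with recall fixed for 3 years.** Null trials, 135 per arm, Poisson model with time offset and diagnosis adjustment; attendance 40% or 60%, ρ = 0, 0.2 or 0.4; 1,500 replicates in each of 18 scenarios.

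| Assumed recall pattern | φ | Poisson SE | Sandwich SE |
|---|---|---|---|
| Weakly tied to diagnosis | 1.57-3.20 | 12.0-26.7% | 4.9-6.7% |
| Strongly tied to diagnosis | 1.23-2.75 | 8.5-26.9% | 4.3-5.8% |
| All on 12-month recall | 0.40-1.09 | 0.3-4.7% | 4.1-5.7% |

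**Step 4: letting recall change.** Same design with 1,000 replicates, an assumed 40/40/15/5% mix and recall unrelated to diagnosis. Attendance probabilities were drawn from beta(50,50), beta(4,4) or beta(2,2), from nearly uniform to widely spread.

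| Recall over 3 years | φ | Type I error, Poisson SE |
|---|---|---|
| Fixed | 1.56 / 1.89 / 2.22 | 9.1 / 15.5 / 20.5% |
| Redrawn each year | 0.87 / 1.15 / 1.40 | 3.4 / 7.3 / 8.8% |
| Settling to 12 months by Year 3 | 0.78 / 0.97 / 1.14 | 2.2 / 5.2 / 6.5% |

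A second set of runs with this mix gave 12-21% with recall fixed, 9-15% with recall partly persistent and 3-11% with recall redrawn yearly, against about 4-8% with robust standard errors throughout. The 9.1% in the table is probably a low draw, since the Step 1 formula gives 11.7% at φ = 1.56.

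**The case against.** The strongest reply is that the documents do not establish over-dispersion. They give neither the distribution of patients over the recall classes nor the spread of attendance. Kept visits are largely limited by recommended visits, which pulls the variance below Poisson. Recall need not be a lasting trait either: E.2.b resets the expected number each year and says severity may change, and Table 6 moves controlled patients to 6 and then 12 months. The model also adjusts for diagnosis, vision impairment and quality of life, and Step 2 shows that strong covariates can remove the excess. All of this stands, and it is why the direction is conditional.

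It does not make the Poisson standard error safe. Table 9's counts are minimums, so the ceiling is not strict. The main drivers named in E.2.b are outside the model or arise after baseline. With ρ = 0.2, Step 2 still gives 12.0% when covariates explain 80% of the recall variance. The conservative case is also fragile: with 5% of patients on 1-2 month recall for 3 years, the rest annual, 40% attendance and the split unexplained by covariates (all assumed), φ is 1.74 at ρ = 0 and 2.41 at ρ = 0.2, with simulated type I error of 13% and 19%.

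It is also fair to say that E.2.e is silent rather than committed to model-based standard errors. Silence leaves the choice open until the data are seen, which is a reason to state it now.

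**Conclusion.** The point holds in conditional form. E.2.e plans a Poisson count model with a time-only offset and no stated variance estimator, in a population whose recommended visits span a sixfold range. If recall differences persist or patients differ in reliability, model-based standard errors are likely too small: roughly 9-21% type I error at an assumed 5% level, for an assumed 40/40/15/5% mix. If recall changes freely, or nearly all patients are on 12-month recall, they can be about right or too large.

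A reader might infer from Table 9 alone that type I error is certainly inflated. The documents do not support that. A range does not fix a variance, and across the assumptions tried in Step 3 the error ran from 0.3% to 26.9%. Nor does the point touch the main Aim 2 conclusion, which rests on the GEE analysis of yearly adherence with each test at alpha 0.025. It is a modest but worthwhile correction to one secondary analysis.

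**What to change.** Add to E.2.e that the appointment-count model will use robust (sandwich) standard errors, with the offset and covariates unchanged. This is preferable to a negative binomial model, which handles only over-dispersion; the sandwich estimator also corrects standard errors that are too large. It gave 4.1-6.7% in the 18 scenarios of Step 3 and about 4-8% in the runs with changing recall. A Pearson-scaled (quasi-Poisson) variance performed similarly in Step 3, at 4.1-7.3%.

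The cost is one phrase and a possibly wider confidence interval for the visit-rate ratio. No extra data or patients are needed.
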